Trial design: Open label, single cohort proof of concept trial. An additional arm of the study will be for subjects treated with the study drug in malignant pituitary tumors. Three clinical trial sites, one at CSMC and the others at Johns Hopkins Hospital and Massachusetts General Hospital.

Study population: Patients will be recruited from the Pituitary Center at Cedars-Sinai Medical Center and the other two sites.

Intervention: lapatinib 1250 mg daily for 6 months. Patients will be treated with the standardized dose used in breast cancer therapy for six months (Cameron & Stein 2008; Geyer et al. 2006). The drug will be supplied by Novartis Oncology.

- a. Primary outcome variable.

Primary outcome in nonfunctioning pituitary adenomas: 40% reduction in tumor size in any dimension. Tumor size and volume will be calculated using Open Source OsiriX® Imaging Software for MacOS. MRIs will be performed at baseline and at 3 and 6 months All MRIs will be centrally read by the dedicated pituitary radiologist at CSMC.

Primary outcome in prolactinomas: 40% reduction in tumor size in any dimension.

Primary outcome in malignant pituitary tumors: Progression free survival

- b. Secondary outcome variables.

Secondary outcomes in prolactinomas:

(a) achievement of 50% reduction of PRL levels (b) PRL normalization (c) percent reduction in PRL levels (d) percent reduction in tumor volume. Tumor volume will be calculated using Open Source OsiriX® Imaging Software for MacOS. (e) correlation of tumor size and PRL reduction (f) clinical predictors of TKI response, including age, gender, duration of disease, dose and duration of dopamine agonist therapy, baseline PRL, and baseline tumor size.

Secondary outcomes in malignant pituitary tumors: partial response, complete response, mortality, 24 hour urine free cortisol levels for Cushing carcinomas, IGF-1 levels for acromegaly carcinomas.

We will correlate ErbB receptor expression with the subjects' clinical response to the study drug. This will be performed through immunohistochemistry staining of pituitary tumor slides from surgery.

Section 5.0. Selection and Withdrawal of Subjects

Inclusion criteria: Subjects with non-functioning pituitary adenomas, who have undergone at least one prior surgical resection and have demonstrated recurrence on MRI.

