Subjects with prolactinomas who are resistant to dopamine agonist therapy who manifest continued tumor size growth while on a dopamine agonist, unless intolerant of adequate doses of a dopamine agonist.

Subjects with malignant pituitary tumors will be eligible for the malignant pituitary tumor arm of the study regardless of existing visual deficits.

Exclusion criteria: Children will be excluded. If subjects have preexisting visual field deficits, they will be monitored on more frequent basis. Patients will also be excluded if they have left ventricular ejection fraction less than 50 %, moderate to severe hepatic impairment (see below for specifics), active hepatitis, HIV positivity, concurrent cancers, life expectancy less than one year, and pregnancy. Pregnant patients will be excluded. Childbearing age women will be required to use

contraception. Patients who become pregnant during the study should discontinue the study immediately.

Withdrawal of Subjects:

Monitoring for adverse effects: Prior to initiating therapy, patients will undergo an echocardiogram and ECG to evaluate the ejection fraction, and the echocardiogram will be repeated every 8 weeks (Visit 3, 5, and 7) and on visit 8. Patients will also undergo ophthalmic testing at visits 1, 4, and 7. Patients with pre-existing stable visual field compromise prior to enrollment will undergo visual field testing at visits 1, 2, and 3, and if stable, then they will proceed with visual field testing every three months for the duration of the study. Patients will be evaluated for adverse effects monthly with physical examinations, chemistry and hematology panels, and ECGs. Adverse events will be graded by the NCI-CTC and include: anorexia, decreased ejection fraction, interstitial lung disease/pneumonitis, diarrhea, nausea, vomiting, hepatotoxicity, rash, and fatigue. Lapatinib will be discontinued in those who developed decreased ejection fraction, who develop pulmonary symptoms, retinal toxicity, worsening of visual fields, and those with toxicity greater than or equal to Grade 2 on the NCI-CTC. [name], from Oncology department at Cedars-Sinai Medical Center, will assist us in monitoring patients for adverse events.

If at any time a patient demonstrates compromise of his visual fields, dilated retinal exam or tumor growth on MRI, he will be withdrawn from the study and referred for surgery.

Section 6.0 Treatment of Subjects

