Patients with recurrent nonfunctioning pituitary tumors or prolactinomas resistant to medical therapy typically undergo surgical resection of the tumor once the tumor demonstrates radiological progression associated with clinical signs and symptoms and/or optic chiasm compression. Otherwise, we observe tumor growth with serial MRIs as long as the chiasm is not compressed until surgery is deemed necessary for decompression of the optic chiasm. In our study, we are excluding any subjects who have compression of the optic chiasm and only will recruit those whom we would otherwise observe with serial MRIs to monitor the tumor growth. After completion of their participation in the study, patients will then resume the standard monitoring of tumor growth. However, if a given patient responds to the study drug and chooses to stay on the drug after cessation of the trial, clinical data will continue to be collected on the patient for further analysis of response to the drug. This will continue until they discontinue to the drug to monitor for safety.

Patients with prolactinomas who are currently being treated by dopamine agonist and patients with malignant tumors on dopamine agonists, somatostatin analogs, and growth hormone receptor antagonist medications prior to enrollment will remain on their drug therapy while on the study drug.

Patients will have a screening visit (visit 1) to determine eligibility for the trial and to assess for exclusion criteria. If the patient meets study criteria for enrollment, he will begin the study drug and be followed in subsequent visits. Study staff will call patients weekly for the first month on the study drug and then every 2 weeks for the second month on the study drug.

The following tests will be done as follows:

On baseline visit 1: time 0
History and physical exam

Draw screening labs: CBC with differential, BMP, LFTs (15 cc blood)
For those with acromegaly from malignant tumors, will GH levels on 2 hour OGTT
For those with ACTH secreting malignant tumors, will check 24 hour urinary free cortisol
Pituitary hormone profile: PRL, TSH, thyroid panel, free T4, IGF-1, LH, FSH,
testosterone (total and free) for males, 8 am cortisol if indicated (total of 15 cc of blood)
Tubes of blood for lab to be frozen (to be used to measure EGFR and Her2 levels) (10 cc)

ECG

Echocardiogram

Check Visual Fields

Dilated retinal exam

Visual acuity check

Ocular pressure check

Color vision test

Urine Pregnancy Test

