Will draw CBC with differential, BMP, LFTs (15 cc blood)
For those with prolactinomas, will also check PRL.
For those with acromegaly from malignant tumors, will check GH levels on 2 hour OGTT
For those with ACTH secreting malignant tumors, will check 24 hour urinary free cortisol
Do ECG
Urine Pregnancy Test
Those with pre-existing visual field compromise, visual field testing

Visit 7: time of 6 months on drug
Physical exam and history
Will draw CBC with differential, BMP, LFTs (15 cc blood)
For those with acromegaly from malignant tumors, will check GH levels on 2 hour OGTT
For those with ACTH secreting malignant tumors, will check 24 hour urinary free cortisol
Pituitary hormones as well—PRL, TSH, thyroid panel, free T4, 8 am cortisol (if indicated), IGF-1, LH, FSH, total and free testosterone for males (15 cc blood)
Tubes for lab for EGFR, her2 levels (10 cc blood)
Do ECG, Echocardiogram
Check visual fields
Dilated retinal exam
Visual acuity check
Ocular pressure check
Color Vision test
Do MRI of pituitary with and without IV gadolinium
Urine Pregnancy Test

Visit 8: time of 1 mo off drug
Physical exam and history
Will draw CBC with differential, BMP, LFTs (15 cc blood)
For those with prolactinomas, will also check PRL.
For those with acromegaly from malignant tumors, will check GH levels on 2 hour OGTT
For those with ACTH secreting malignant tumors, will check 24 hour urinary free cortisol
Draw tubes for EGFR, Her2 levels (10 cc blood)
Do ECG, Echocardiogram

Urine Pregnancy Test

Note: Study visits may be conducted over 2 days to allow for sufficient time to complete the procedures, scheduling availability, and patient preference.

Study procedure flowsheet:

(See following page)

Procedure	Baseline Visit	Visit #2 (+30 days)	Visit #3 (+60 days)	Visit #4 (+90 days)	Visit #5 (+120 days)	Visit #6 (+150 days)	Visit #7 (+180 days)	Visit #8** (+210 days)
Laboratory Blood Tests (may include levels of hormones, cholesterol, CBC, and metabolic panel)	X	X	X	X	X	X	X	X
MRI of the Pituitary	X^^			X			X	
Echocardiogram	X		X		X		X	X
Electrocardiogram (ECG)	X	X	X	X	X	X	X	X
Visual Field Test	X	X^	X^	X		X^	X	
History and Physical	X	X	X	X	X	X	X	X
Informed Consent	X							
Color Vision Test	X			X			X	
Ocular Pressure Check	X						X	
Visual Acuity	X						X	
Dilated Retinal Exam	X			X			X	
Hormonal profile	X	X	X	X	X	X	X	X
Oral Glucose Tolerance Test (OGTT) (malignant arm)	X*	X*	X*	X*	X*	X*	X*	X*

24-hour Urinary Free Cortisol (malignant arm)	X+							

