who received lapatinib and 7% in those on placebo. Risks of adverse events are not additive or cumulative. SAEs were reported in 6% of those on lapatinib compared to 5% on placebo. Cardiac events including left ventricular ejection fraction decreases were reported in approximately 1% of patients and most have partial or full recovery. Symptomatic decreases in ejection fraction were observed in approximately 0.3% of patients on lapatinib. Interstitial lung disease is observed in 0.2% of patients. Hepatotoxicity has been observed in <1% of patients. Grade 3 and 4 diarrhea occurs in <10% of patients. Nausea may be seen in 18% of patients and rash in 29% (Investigators' Brochure).

2. Prior to initiating therapy, patients will undergo an echocardiogram and ECG to evaluate the ejection fraction, and the echocardiogram will be repeated every 8 weeks and on visit. Patients will be evaluated for adverse effects monthly with physical examinations, chemistry and hematology panels, and ECGs. Adverse events will be graded by the NCI-CTC. Common adverse events include: hand-foot syndrome, rash, diarrhea, indigestion, nausea, vomiting, anorexia, anemia, low platelets, abnormal liver tests (ALT (SGPT) level raised, AST/SGOT level raised, hyperbilirubinemia, backache, pain in limb, insomnia, fatigue, and shortness of breath. Rare but serious events include: heart failure (depression of left ventricular systolic function), abnormal heart beat (prolonged QT interval), liver damage (hepatotoxicity), and lung problems (interstitial lung disease/pneumonitis). Lapatinib will be discontinued in those who developed decreased ejection fraction, who develop pulmonary symptoms. Those subjects with toxicity less than or equal to Grade 2 on the NCI-CTC will have their dose held and resumed when the toxicity has resolved. Those subjects with toxicity equal to Grade 3 on the NCI-CTC will have their dose held and resumed at a fifty percent dose reduction when the toxicity has resolved. Those subjects with toxicity equal to Grade 4 on the NCI-CTC will be discontinued on the study drug. [name], from Oncology department at Cedars-Sinai Medical Center, will assist us in monitoring patients for adverse events.
3. If at any time a patient demonstrates a worsening of their visual fields or tumor growth on MRI, they will be withdrawn from the study and referred for surgery.

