For any other NCI-CTCAE v3.0 Grade 3 or 4 adverse events or any clinically significant, lower-grade adverse event, treatment with lapatinib should be interrupted for a maximum of 14 days until the patient recovers completely or the adverse event reverts to NCI-CTCAE v3.0 Grade 1 or to baseline grade. If recurrence of adverse event after drug holiday / interruptions is observed a dose reduction by 250mg is recommended. Dose reduction should only be implemented when all supportive care measures have been exhausted without an improvement of patient status. Lapatinib should not be used at doses below 1000mg if given as monotherapy or 750mg in combination with trastuzumab. In all cases where the subject is withdrawn due to unusual or unusually severe adverse event considered related to lapatinib, the investigator must report the withdrawal as an SAE and on the CRFs.

Table 1 Summary of dose holding/interruptions and dose de-escalation recommendations for GW572016 (lapatinib) in case of lapatinib related adverse events (graded according to NCI-CTCAE v3.0)

Adverse events	Action
Non-hematological, Grade 1 or 2	Continue lapatinib therapy at full dose prescribed (see adverse events management instructions section Error! Reference source not found. Apply maximum supportive care recommendations (see Error! Reference source not found.) If prolonged duration of Grade 2 adverse event is affecting quality of life a one-time decrease of dose by 250 mg is allowed.

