Non-hematological, Grade 3 or 4	Apply maximum supportive care recommendations (see section Error! Reference source not found.) Hold lapatinib therapy until recovery to Grade \leq 1 (up to 14 days). Refer to events management instructions Section Error! Reference source not found. Grade 3 or 4 left ventricular cardiac dysfunction - please refer to specific section Error! Reference source not found. For NCI-CTCAE v3.0 Grade 3 or 4 interstitial pneumonitis or Grade 4 rash manifested as toxic epidermal necrolysis (e.g. Stevens-Johnson Syndrome etc) lapatinib must be permanently discontinued If recurrence of adverse event after drug hold / interruptions is observed, and maximum supportive care measures applied, a dose reduction by 250mg is recommended. Lapatinib should not be used at doses below 1000mg if given as monotherapy or 750mg in combination with trastuzumab. NOTE: The 750 mg dose should only be used after all supportive measures have been exhausted. (If administered in combination with paclitaxel refer to table 13)
Non-hematological, Grade 3 or 4 and adverse events NOT resolved to Grade \leq 2 within a maximum of 2 weeks from last planned administration	Action (discontinue or resume lapatinib therapy) in individual cases to be decided by the Executive Committee. Dose reductions by 250mg (up to 2 reductions) will be considered after maximum supportive care recommendations (see Error! Reference source not found.) are introduced.

Cardiac* (asymptomatic drop in LVEF or symptomatic congestive heart failure)
	
Lapatinib therapy to be discontinued permanently in case of symptomatic NYHA class III and IV CHF. Lapatinib therapy to be hold continued or resumed according to Figure 1 for patients with NYHA class I or II CHF.

Hematological adverse events: Absolute neutrophil count (ANC) <1.0 x 10⁹/L Platelets <75 x 10⁹/L Hemoglobin <9.0 g/dL (after transfusion if needed)
	
Hold chemotherapy if lapatinib given simultaneously; if the adverse event is related to chemotherapy please refer to appropriate label (until recovery to Grade ≤1). If ANC recovers to 1.5 x 10⁹/L within 7days, then merely delaying dose is acceptable. If no recovery to ANC of 1.5 x 10⁹/L within 7 days then decrease chemotherapy dose by 20%. Dose modifications for thrombocytopenia, at the start of subsequent courses of therapy are the same as recommended for neutropenia above. Next cycle should not begin until the platelet count has recovered to 100 x 10⁹/L or more.

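### The protocol's general toxicity rules for lapatinib contradict each other at Grades 2, 3 and 4, and for cytopenia Table 1 does not settle which applies because its hematological row is written for chemotherapy

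*Combined protocol and SAP*

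**What the plan says.** The regimen in Section 4.0 is "Intervention: lapatinib 1250 mg daily for 6 months". Section 6.0 lets subjects stay on hormonal background treatment: dopamine agonists and, in the malignant arm, also somatostatin analogs and "growth hormone receptor antagonist medications prior to enrollment will remain on their drug therapy while on the study drug". Chemotherapy is in neither list.

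Three places tell the site what to do with lapatinib for toxicity in general.

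- Section 5.0, *Withdrawal of Subjects*, discontinues lapatinib in "those with toxicity greater than or equal to Grade 2 on the NCI-CTC".
- Section 8.0, item 2, holds and then resumes the drug at Grade 2 or lower. For Grade 3 it says "toxicity equal to Grade 3 on the NCI-CTC will have their dose held and resumed at a fifty percent dose reduction". For Grade 4 it says "toxicity equal to Grade 4 on the NCI-CTC will be discontinued on the study drug".
- Section 8.0, *Other adverse events*, begins "For any other NCI-CTCAE v3.0 Grade 3 or 4 adverse events or any clinically significant, lower-grade adverse event". For these it interrupts lapatinib for at most 14 days, until full recovery or a return to Grade 1 or baseline. It recommends a 250 mg reduction if the event recurs and sets a monotherapy floor of 1000 mg.

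Table 1, which is titled as lapatinib dose guidance for lapatinib-related events, has a hematological row triggered by ANC below 1.0, platelets below 75 (both x 10⁹/L) or hemoglobin below 9.0 g/dL. Its action column opens "Hold chemotherapy if lapatinib given simultaneously; if the adverse event is related to chemotherapy please refer to appropriate label". It goes on to a 20% cut in the chemotherapy dose and a platelet condition for starting the next cycle.

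*Dose Delays and Dose Reductions* allows a delay of up to 2 weeks for toxicity and one dose reduction per subject. It requires the medical monitor to be consulted before any dose change or before continuing after a longer delay.

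**The concern.** The three general rules cannot all be followed, and no sentence says which one governs. For the same event, sites could stop the drug, resume it at half dose, or interrupt it and resume, each with a protocol sentence in support. With three sites, this is a matter of subject safety and of consistent dosing.

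Cytopenia shows the problem clearly. Section 8.0 lists anemia and low platelets among the common adverse events, and a blood count is scheduled at every visit. A site with a low count would naturally turn to the hematological row of Table 1. That row has no instruction about lapatinib, so the site returns to the conflicting general rules.

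**Working it through.** There is no planned figure to reproduce. The check sets the rules side by side and works out the doses.

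**Inputs.** Full dose 1250 mg (Section 4.0). Tablet strength 250 mg (*Pharmaceutical Information*). Monotherapy floor 1000 mg and reduction step 250 mg (*Other adverse events*). One reduction per subject (*Dose Delays and Dose Reductions*). Visits 30 days apart, within 7 days (Section 6.0).

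**Step 1: the rules by grade.**

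| Grade | Section 5.0 | Section 8.0, item 2 | *Other adverse events* |
|---|---|---|---|
| 2 | Discontinue | Hold, then resume | Interrupt up to 14 days if clinically significant |
| 3 | Discontinue | Hold, then resume at 50% | Interrupt up to 14 days; 250 mg cut on recurrence |
| 4 | Discontinue | Discontinue | Interrupt up to 14 days |

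At Grades 2 and 3 all three differ. At Grade 4 the first two agree and the third does not.

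**Step 2: the halved dose.**

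- 0.50 x 1250 = 625 mg.
- 625 / 250 = 2.5 tablets.
- 1000 - 625 = 375 mg below the floor.
- One 250 mg step gives 1250 - 250 = 1000 mg, exactly the floor.

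The halved dose therefore breaks the floor, while the single permitted 250 mg step respects it.

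**Step 3: does Table 1 settle it for cytopenia?** The hematological row holds chemotherapy, refers to its label, cuts its dose by 20%, and delays later courses and cycles. One clause permits a delayed dose without naming a drug, but the sentences around it are about chemotherapy. No clause holds, reduces, resumes or stops lapatinib. The rows that give general lapatinib hold and reduction actions are headed as non-hematological. The last cell caps time off lapatinib at 21 days in any 90, which limits a hold but does not call for one.

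**Step 4: does *Dose Delays and Dose Reductions* settle it?** Its delay limit and single reduction fit *Other adverse events*. It does not say that they override Section 5.0 or item 2 of Section 8.0.

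**Step 5: can recovery be confirmed at scheduled visits?** The shortest permitted gap between visits is 30 - 7 = 23 days. If a hold starts from a scheduled count, the next one falls outside the 14-day limit, so an unscheduled count is needed.

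**The case against.** The strongest reply is that the hematological row is harmless leftover text. Its opening instruction is conditional on chemotherapy, so without chemotherapy it has little effect, and the body text does reach cytopenia. *Other adverse events* and *Dose Delays and Dose Reductions* together give a workable path: hold for up to 14 days, take one 250 mg step with the medical monitor's involvement, and in general withdraw subjects whose toxicity has not resolved. Most of this stands. The row alone would call only for tidying, and the stop-or-resume consequences come from the general conflict. The reply does not remove that conflict, because the workable path contradicts Section 5.0 and item 2 of Section 8.0 and nothing ranks them.

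Three stronger readings are tempting, and the documents do not support them.

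- A reader might infer that a subject with cytopenia has no lapatinib guidance at all. The gap is in the table. The general rules apply to cytopenia, and the trouble is that they disagree.
- A reader might infer that *Other adverse events* leaves the resumption dose open. It prints no number, but it ties reduction to recurrence and to exhausted supportive care, so the natural reading is that a first episode resumes at the previous dose.
- A reader might infer that any count below a printed cutoff should trigger a hold whatever its grade, and that the medical monitor should be consulted before every restart. No text supports either, and resuming a recovered subject without that contact is not shown to be an error.

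**Conclusion.** The point holds as an internal contradiction in the dosing rules. At each of Grades 2, 3 and 4 at least two of the three rules disagree, and one of them prescribes a dose 375 mg below the protocol's own floor. Table 1 does not resolve this for cytopenia. It should be corrected, because a safety rule that cannot be followed as written is more than missing detail.

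The conclusion rests on two readings: that no chemotherapy is given (it is absent from the regimen and from the retained drugs, though not expressly prohibited), and that the general rules cover cytopenia, which has no section of its own in the body text.

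The frequency cannot be sized. The documents give no cytopenia rate on lapatinib monotherapy and do not map the three laboratory cutoffs to toxicity grades, so it cannot be shown which disagreement a given cutoff would trigger. A reader might also infer that the efficacy analysis is compromised. Neither the endpoint definitions nor the sample size calculation uses these rules.

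**What to change.** 1. State one governing rule for toxicities without a section of their own, and make Section 5.0 and item 2 of Section 8.0 match it. For events that *Other adverse events* covers, interrupt lapatinib for up to 14 days until Grade 1 or baseline. Resume at 1250 mg or, with the medical monitor's agreement, at 1000 mg as the single permitted reduction. Discontinue at Grade 4, as Section 5.0 and item 2 already do. *Other adverse events* and the Grade 3-4 row of Table 1 then need their Grade 4 wording aligned.
2. Delete the 50% reduction from item 2 of Section 8.0.
3. Delete the chemotherapy, 20% and next-cycle text from the hematological row and refer that row to the governing rule. Repeat there that Grade 4 laboratory values are reported as SAEs, as *Additional SAE definitions* requires.

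While editing, correct the Table 1 row for unresolved Grade 3-4 events, which contemplates up to two 250 mg reductions. That would give 1250 - 500 = 750 mg, below the floor and one step more than the single reduction allowed.

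Do not add a grade-independent hold or mandatory consultation before every resumption.

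The change is to wording. Each cytopenia hold needs an unscheduled blood count, which Section 8.0, item 4, already allows as additional laboratory testing. The main downside is that some subjects who recover from Grade 2 or 3 toxicity would resume lapatinib where Section 5.0 would have stopped it, and the sponsor should accept that knowingly.
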